#### **2.2 SECONDARY ENDPOINTS**

The secondary endpoints include an evaluation of the following adverse events per INTERMACS definitions (version 5.0) throughout the study period:

- Stroke (ischemic/hemorrhagic)
- Pump thrombosis
- Major bleeding
- GI Bleeding
- Peripheral arterial thromboembolic events
- Transient ischemic attack
- Hemolysis
- Venous thromboembolism
- Myocardial infarction
- Right heart failure
- Cardiac arrhythmias
- Liver and kidney dysfunction
- Death due to any cause

### 3 STUDY DESIGN

A prospective, single-center, randomized controlled trial of the feasibility and safety of apixaban in HeartMate 3 patients.

### 3.1 STUDY CENTER AND PATIENTS

Eligible patients implanted with HeartMate 3 LVAS and meeting predefined criteria will be included in this study. The study will be conducted at the Institute for Clinical and Experimental Medicine in Prague and will be made open to other selected centers. The study design anticipates 45 patients to be enrolled.

### 3.2 STUDY DURATION

Patients enrolled will be followed-up for 90 days post-transition to a designated antithrombotic regimen based on randomization. Provided the individual patients clinical course is uneventful regarding the primary endpoint, the patient's follow-up within the antithrombotic study protocol will be extended to the next pre-specified time point for analysis at 180 days. After the 180 days timepoint is reached, the patients will be given a chance to prolong the study until 1 year. All apixaban subsets will be treated according to their original study arm, the patients from the Vitamin K antagonist and aspirin group will be randomized in a 1:1 manner to apixaban with or without aspirin.

If the individual uneventful primary safety endpoint is established, the patient follow-up will be prolonged with next pre-specified time point for analysis at 1 year. If the second safety endpoint is reached, the patients could be followed for the duration of support with the HeartMate 3.

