### 2 STUDY OBJECTIVES

#### 2.1 PRIMARY ENDPOINT

The primary endpoint to evaluate the safety and feasibility of apixaban with the HeartMate 3 LVAS is survival free of major HRAEs (hemocompatibility related adverse events) at 90 days post-enrollment. The primary analysis will compare the apixaban groups (n=30) to control (n=15). A separate analysis will compare the primary endpoint in patients randomized to receive aspirin (n=15) and no-aspirin (n=15) within the apixaban group.

Major HRAEs include:

- Stroke (ischemic/hemorrhagic)
- Pump thrombosis
- Severe bleeding (see Appendix II)
- Peripheral arterial thromboembolic events

HRAEs are influenced by several patient-specific risk factors, including anticoagulation, poor general health, altered circulation, the pump's hemocompatibility, and the presence of other comorbidities (e.g., AF, infections, etc.). In standard use, clinicians balance the risk of stroke and other thromboembolic (TE) events with the increased risk of bleeding when prescribing

anticoagulation or antiplatelet medications. Therefore, a composite endpoint comprising TE, bleeding, and pump-related events were chosen for the analysis.

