#### 5.3 DATA ANALYSIS AND STATISTICAL ISSUES

Survival free of a hemocompatibility-related endpoint 90 days will be evaluated. The prevalence (percent of patients with events) and incidence (event rates in events per pt-year) of adverse events and rehospitalizations will be determined.

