## DOT HM3 Study – Statistical analysis plan

Stable HM3 patients who have not suffered a Major hemocompatibility-related adverse after index hospitalization discharge and are at least 3 months post-implant will be screened for participation in the study. Upon meeting the study criteria and patient informed consent, the individuals will be randomized to either continued therapy with a Vitamin K antagonist and aspirin or conversion to apixaban 5 mg twice a day in a 1:2 manner; the apixaban group will be stratified further by 1:1 randomization to continued use of 100 mg aspirin once daily or cessation. Thus, 45 patients are planned to be enrolled and randomized in 3 subgroups of 15 patients in each arm. The sample size of 45 patients was calculated to be sufficient to elucidate any safety signal. After 180 days follow-up is reached, the Vitamin K antagonist and aspirin arm will be transitioned to apixaban and randomized in a 1:1 manner to groups with or without aspirin.

Survival free of a hemocompatibility-related adverse events event (Stroke ischemic/hemorrhagic, Pump thrombosis, Severe bleeding, Peripheral arterial thromboembolic events) at the endpoint of 90 days will be evaluated as primary endpoint as proportion of success calculated between the apixaban and the warfarin arms. The prevalence (percent of patients with events) and incidence (event rates in events per pt-year) of adverse events and rehospitalizations will be determined. The secondary endpoints include an evaluation of the following adverse events per INTERMACS definitions (version 5.0) throughout the study period:

- Stroke (ischemic/hemorrhagic)
- Pump thrombosis
- · Major bleeding
- GI Bleeding
- Peripheral arterial thromboembolic events
- Transient ischemic attack
- Hemolysis
- Venous thromboembolism
- Myocardial infarction
- Right heart failure
- Cardiac arrhythmias
- Liver and kidney dysfunction
- Death due to any cause

Time to event analyses will be done by Kaplan-Meier analysis. The overall outcomes being evaluated for clinical safety as assessed by the study's oversight committee.

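### Follow-up beyond day 90 is promised only to patients without a primary-endpoint event, so later deaths, adverse events and rehospitalisations in the others are not provided for

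*Protocol*

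**What the plan says.** Protocol section 3.2 sets the common period: "Patients enrolled will be followed-up for 90 days post-transition to a designated antithrombotic regimen based on randomization". The step to day 180 is conditional on the patient's own outcome: "Provided the individual patients clinical course is uneventful regarding the primary endpoint, the patient's follow-up within the antithrombotic study protocol will be extended". The step to 1 year is optional for the patient ("After the 180 days timepoint is reached, the patients will be given a chance to prolong the study until 1 year") and carries an outcome condition again: "If the individual uneventful primary safety endpoint is established, the patient follow-up will be prolonged with next pre-specified time point for analysis at 1 year".

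The primary endpoint is "survival free of major HRAEs (hemocompatibility related adverse events) at 90 days post-enrollment" (Protocol 2.1). The secondary endpoints, which include death from any cause, have no 90-day limit: "The secondary endpoints include an evaluation of the following adverse events per INTERMACS definitions (version 5.0) throughout the study period" (Protocol 2.2, repeated in the SAP). The summary measures are given in Protocol 5.3 and again in the SAP: "The prevalence (percent of patients with events) and incidence (event rates in events per pt-year) of adverse events and rehospitalizations will be determined". The SAP adds "Time to event analyses will be done by Kaplan-Meier analysis" and gives no censoring rule.

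Three other sections bear on patients who have had an event. Protocol 3.3.2 has the Expert Advisory Committee judge, after an HRAE, whether the patient can safely stay on the assigned arm. Protocol 5.2.8 lists the possible outcomes as transplant, death, explant or withdrawal. Protocol 5.2.9 returns patients to their pre-study regimen when follow-up ends and describes no data collection after that.

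**The concern.** Under section 3.2 as written, a patient with a severe bleed on day 30 is observed to day 90 and no further. A death, stroke, haemolysis or readmission on day 120 in that patient is not in the 180-day data. Whether a patient is still observed on days 91–180 then depends on a post-randomisation outcome that treatment may affect, so the groups still under observation are no longer the randomised groups. A Kaplan-Meier curve for death to day 180 would censor at day 90 exactly the patients who had an early stroke, pump thrombosis, severe bleed or arterial embolism, and that censoring may be informative.

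This is a safety trial with 15 patients per arm, where one or two unseen deaths change the picture. Data that were never collected cannot be restored by analysis. Day 180 is also the last time point with a randomised warfarin comparator, because the control arm then moves to apixaban (Protocol 3.3.1).

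**Working it through.** **No figure in the plan to reproduce.** Only the allocation can be checked: 3 × 15 = 45, and 45 × 2/3 = 30 on apixaban. Neither document gives an event rate, so every rate below is an assumption shown over a range.

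**Which results are affected**
- 90-day primary endpoint: unaffected, because everyone is followed for 90 days.
- Time to first major HRAE to day 180: unaffected if all randomised patients stay in the analysis, since an early failure remains a failure. At 10% risk per 90 days, the 180-day risk is 1 − 0.90 × 0.90 = 19% under either follow-up rule.
- Deaths after a non-fatal HRAE, first occurrences of other components, recurrent events, other adverse events and rehospitalisations after day 90: not collected for patients with an early event.

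**Event rates.** Let p be the 90-day risk of a first HRAE at constant hazard, with cumulative hazard H = −ln(1 − p) per 90 days. Let the hazard be multiplied by k after a first event. Deaths are ignored in this step.
- Expected events in 90 days for a patient who starts event-free: E = p + k(H − p).
- Expected events on days 91–180 if everyone is followed: F = p·k·H + (1 − p)·E.
- Rate as collected, in either window: E × 365.25/90.
- Full-follow-up rate, days 91–180: F × 365.25/90.
- Full-follow-up rate, days 0–180: (E + F) × 365.25/180.

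Worked case, p = 15% and k = 3: H = 0.1625; E = 0.15 + 3 × 0.0125 = 0.1876; F = 0.15 × 3 × 0.1625 + 0.85 × 0.1876 = 0.2326. The collected rate is 0.76 per patient-year, against 0.94 (days 91–180) and 0.85 (days 0–180).

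| p | k | Collected | Full, days 91–180 | Too low by | Full, days 0–180 | Too low by |
|---|---|---|---|---|---|---|
| 5% | 2 | 0.213 | 0.224 | 5% | 0.218 | 2% |
| 5% | 3 | 0.219 | 0.239 | 8% | 0.229 | 4% |
| 10% | 2 | 0.449 | 0.490 | 8% | 0.470 | 4% |
| 10% | 3 | 0.471 | 0.552 | 15% | 0.512 | 8% |
| 15% | 2 | 0.710 | 0.802 | 11% | 0.756 | 6% |
| 15% | 3 | 0.761 | 0.944 | 19% | 0.852 | 11% |
| 20% | 2 | 1.000 | 1.162 | 14% | 1.081 | 8% |
| 20% | 3 | 1.093 | 1.418 | 23% | 1.256 | 13% |

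At k = 1, E = F = H and the rates are unbiased. Counts are still short: at p = 15% and k = 1, 45 × 2 × 0.1625 = 14.6 events occur and 45 × (1 + 0.85) × 0.1625 = 13.5 are collected.

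**Deaths.** Further assumption: 5% mortality over 180 days in event-free patients. Missed deaths = patients stopped × (1 − 0.95^(k/2)).
- p = 10%, k = 1: 4.39 × 0.0253 = 0.11 missed of 2.25.
- p = 10%, k = 3: 4.27 × 0.0741 = 0.32 missed of 2.67.
- p = 20%, k = 3: 8.54 × 0.0741 = 0.63 missed of 3.07.

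**Between-arm difference** (apixaban p = 20%, control p = 10%)
- k = 3 in both arms: the day 91–180 difference is 0.866 with full follow-up and 0.622 as collected, so it shrinks. Over days 0–180 it is 0.744 against 0.622.
- k = 1 on apixaban and k = 3 on control: 0.353 with full follow-up and 0.434 as collected, so it grows.

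**Patients concerned.** 45 × 5% = 2.25 and 45 × 20% = 9, so roughly 2 to 9.

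**The case against.** The strongest reply is textual. The condition in section 3.2 attaches to follow-up within the antithrombotic protocol, which could mean only that the assigned regimen stops while observation goes on. Section 3.3.2 fits that reading, since a committee decision about staying on the arm has little purpose after day 90 if eventful patients leave automatically. So does section 5.2.8, whose outcome list has no entry for follow-up ended because of an HRAE. This stands as far as it goes: the text is ambiguous, and it cannot be stated as fact that eventful patients will be lost. But no section says they are kept under observation, so sections 2.2, 3.2, 3.3.2 and 5.2.8 need reconciling on either reading.

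A second reply concerns size. The secondary endpoints cover the whole study and the first 90 days are complete, so quoting days 91–180 alone roughly doubles the apparent bias. That is correct, and the day 0–180 figures are the fairer summary. The expected number of missed deaths is also below one in the cases shown, which is small against chance variation in 45 patients.

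A reader might go further and infer that the rule dilutes any true excess of harm on either regimen. The documents do not support that. It requires a similar rise in risk after an HRAE in both arms, and the second example above shows the opposite. Nor can it be inferred that rates are understated in both arms, because an arm with k = 1 has an unbiased rate.

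**Conclusion.** The gap is real and should be fixed, but it does not undermine the main result. As written, follow-up beyond day 90 is selected on outcome, while secondary endpoints that need complete follow-up run past that point. Counts and percentages of all randomised patients are understated for any post-event risk above zero. Rates per patient-year are understated only if risk rises after a first HRAE. The documents do not state such a rise, although excluding patients with a prior major HRAE (Protocol 4.2) is consistent with it. The direction of bias in the between-arm contrast is unknown.

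The size, about 2–13% over days 0–180, rests wholly on assumed 90-day risks of 5–20%, a constant hazard and a two- to three-fold increase after a first event. At 1 year the same selection applies, with patient choice added. A reader might take the 1-year warfarin comparison to be spoiled by this rule, but no randomised warfarin comparator exists after day 180 under any follow-up rule.

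**What to change.** In Protocol 3.2, separate outcome follow-up from study treatment. State that every randomised patient is followed to day 180 for vital status, INTERMACS adverse events and rehospitalisation, whatever the regimen and whether or not a primary-endpoint event has occurred. End that follow-up only for death, transplant, explant or withdrawn consent. Reconcile section 3.2 with 2.2, 3.3.2 and 5.2.8 so that a decision about the assigned arm does not end data collection. This says nothing about which treatment a patient should receive after an event.

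In the SAP, analyse the 180-day secondary endpoints by randomised arm with all randomised patients as the denominator, and state the censoring rules for the Kaplan-Meier analyses. Where eventful patients were not followed, label results after day 90 as conditional on being event-free at day 90.

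The cost is a short amendment and about 90 more days of observation for roughly 2–9 patients at the assumed risks, with no new procedure.

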### 3.3 STUDY DESIGN

### 3.3.1 Study design

Stable HM3 patients who have not suffered a Major hemocompatibility-related adverse event after index hospitalization discharge and are at least 3 months postimplant will be screened for participation in the study. Upon meeting the study criteria and patient informed consent, the individuals will be randomized to either continued therapy with a Vitamin K antagonist and aspirin or conversion to apixaban 5 mg twice a day in a 2:1 manner (dose targeted to renal function); the apixaban group will be stratified further by 1:1 randomization to continued use of 100 mg aspirin once daily or cessation. Thus, 45 patients are planned to be enrolled and randomized in 3 subgroups of 15 patients in each arm (see Appendix I). After 180 days follow-up is reached, the Vitamin K antagonist and aspirin arm will be transitioned to apixaban and randomized in a 1:1 manner to groups with or without aspirin.

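### The secondary endpoints, event rates and Kaplan-Meier curves have no last day for apixaban versus VKA, although controls move to apixaban after day 180

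*Protocol*

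**What the plan says.** The primary endpoint is tied to day 90 in Protocol 2.1 and 5.3 and in the SAP. Nothing else has a closing day:

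- **Secondary events, including death.** Protocol 2.2: "The secondary endpoints include an evaluation of the following adverse events per INTERMACS definitions (version 5.0) throughout the study period". The SAP repeats this. Neither document defines the period.
- **Percentages and rates.** Protocol 5.3: "The prevalence (percent of patients with events) and incidence (event rates in events per pt-year) of adverse events and rehospitalizations will be determined". The SAP repeats this, again without a window.
- **Kaplan-Meier.** The SAP names the method for time-to-event analyses but gives no horizon and no censoring rule at the switch.

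The control treatment does end on a known day. Protocol 3.3.1: "After 180 days follow-up is reached, the Vitamin K antagonist and aspirin arm will be transitioned to apixaban". The SAP agrees, and Protocol 3.2 adds that "the patients from the Vitamin K antagonist and aspirin group will be randomized in a 1:1 manner to apixaban with or without aspirin". Follow-up may outlast that day: "the patients will be given a chance to prolong the study until 1 year", and later "the patients could be followed for the duration of support with the HeartMate 3". Protocol 3.2 names both day 180 and 1 year as analysis time points. It does not say that the comparison with VKA stops at the first of these.

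Section 3.2 also makes follow-up past day 90 conditional: "Provided the individual patients clinical course is uneventful regarding the primary endpoint". A second event-free condition precedes the 1-year point: "If the individual uneventful primary safety endpoint is established, the patient follow-up will be prolonged".

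**The concern.** After the switch, the control arm carries no further information about VKA. A summary by original arm over the whole study period sets apixaban against a mixture of VKA and apixaban, and the mixture contains more apixaban the longer follow-up lasts. With constant rates the contrast shrinks toward no difference in either direction, so both an excess and a reduction of events on apixaban would be understated. That matters in a safety study whose SAP says 45 patients are enough to bring out a safety signal, because the secondary events are part of that reading.

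A smaller question concerns the conditions on continuing. Section 3.2 does not separate staying on protocol treatment from being observed. If observation stops after an early hemocompatibility event, later events and deaths in those patients are lost and the censoring is informative. The effect is probably modest, and its direction depends on which arm has more early events.

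**Working it through.** The plan has no figure to reproduce here. The sample size of 45 comes without an event rate, effect size or power. The calculation asks how far a true apixaban:VKA rate ratio would be distorted if the arms were compared as randomised beyond day 180.

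**Inputs from the documents:** 15 controls and 30 apixaban patients (Protocol 2.1); switch after day 180 (Protocol 3.2, 3.3.1, SAP); follow-up to 1 year and possibly beyond (Protocol 3.2).

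**Assumptions:** event rates constant over time; no transient effect of switching; no differential depletion; everyone observed to day 180; controls who do not continue are censored at day 180. The VKA rate *r* is taken as 0.25 to 1.0 per patient-year and the true rate ratio RR as 2.0 or 0.5.

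**Control person-time.** If all continue to day 365, controls have 15 × 180 = 2,700 patient-days on VKA and 15 × 185 = 2,775 on apixaban. VKA makes up 2,700/5,475 = 49% of control time. At day 730 it is 180/730 = 25%.

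**Rate ratio by original arm.** With *f* the share of controls continuing and *T* the last day:

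observed RR = RR × [180 + f(T − 180)] / [180 + f(T − 180) × RR]

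For T = 365, f = 1, RR = 2 this is 2 × 365/(180 + 370) = 730/550 = 1.327. If only controls event-free at day 180 continue, f = exp(−r × 180/365).

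| Last day | Controls continuing | f | True 2.0 appears as | True 0.5 appears as |
|---|---|---|---|---|
| 180 | not applicable | – | 2.000 | 0.500 |
| 365 | all | 1 | 1.327 | 0.670 |
| 365 | event-free, r = 0.25 | 0.884 | 1.355 | 0.656 |
| 365 | event-free, r = 0.5 | 0.781 | 1.384 | 0.643 |
| 365 | event-free, r = 1.0 | 0.611 | 1.443 | 0.619 |
| 365 | half | 0.5 | 1.493 | 0.602 |
| 365 | half of event-free, r = 0.25 to 1.0 | 0.442 to 0.305 | 1.524 to 1.614 | 0.593 to 0.568 |
| 730 | all | 1 | 1.141 | 0.802 |
| 730 | half | 0.5 | 1.247 | 0.717 |

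**Kaplan-Meier, first event by day 365.** The apixaban estimate is 1 − exp(−RR × r). The control estimate is 1 − exp(−r) without the switch and 1 − exp[−r(180 + 185 × RR)/365] with it. For r = 0.5 and RR = 2, apixaban is 63.2% and control is 39.3% without the switch or 52.9% with it. The gap falls from 23.9 to 10.3 points.

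| r | RR = 2: true gap → seen | RR = 0.5: true gap → seen |
|---|---|---|
| 0.25 | 17.2 → 8.0 | 10.4 → 5.3 |
| 0.5 | 23.9 → 10.3 | 17.2 → 9.0 |
| 1.0 | 23.3 → 8.6 | 23.9 → 13.3 |

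Under the censoring assumption these gaps do not depend on *f*, because everyone still at risk in the control arm after the switch is on apixaban. A simulation at r = 0.5, RR = 2 gave control estimates of 53.0%, 53.0% and 52.7% for f = 1, 0.5 and 0.2, against 52.9% from the formula.

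**Precision, for context.** To day 180 the arms contribute about 7.4 and 14.8 patient-years. At 0.5 per patient-year in both arms, that is about 3.7 and 7.4 expected events. The 95% interval for the rate ratio spans a factor of exp[1.96 × √(1/3.7 + 1/7.4)], about 3.5, each way. To day 90 the factor is about 5.8.

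**The case against.** The strongest reply is that the plan never prescribes the comparison being criticised. The only between-arm calculation the SAP spells out is the 90-day primary endpoint. The rates and curves are simply to be produced, with no test or hazard ratio named. Day 180 is a named analysis time point with the switch right after it, so a 180-day randomised phase followed by an optional extension is a natural reading. This stands in part: the full-period contrast is implied, not stated. But the secondary events run over an undefined study period, 1 year is named as an analysis time point in the same way as day 180, and no passage ends the VKA comparison at the switch.

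Other points also have force. A Kaplan-Meier curve is sound up to day 180 even if drawn further. All rates and continuation shares above are assumed, and the 2-year figures rest on a clause that only permits such follow-up. No passage says that controls who decline to continue are censored at day 180. The trial is also imprecise: a distortion of at most 1.5-fold at 1 year (2.0 to 1.33) is smaller than the 3.5-fold uncertainty to day 180. These points limit how much weight the figures can bear. They do not justify an avoidable bias on top of the imprecision.

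On observation after an early event, Protocol 3.3.2, 5.2, 5.2.8 and Appendix III suggest that events and outcomes are still recorded. No passage says so outright, and Protocol 5.2.9 ties the end of follow-up to a change of regimen. This part is a request for clarification.

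**Conclusion.** The concern holds and should be fixed before analysis. Read literally, the plan allows apixaban-versus-VKA summaries over a period in which the control arm is no longer on VKA. Under constant rates, a true doubling would appear at 1 year as a ratio of 1.33 if all controls continue and up to about 1.6 if few do; a true halving would appear as 0.67 to 0.57. One-year Kaplan-Meier gaps would shrink to roughly 36% to 56% of their true size (8.6/23.3 to 13.3/23.9). The direction follows from the design given constant rates; the size depends on assumed rates and continuation. The 90-day primary endpoint, and anything read at or before day 180, is not affected by the switch.

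**What to change.** 1. In Protocol 2.2 and the SAP, limit all apixaban-versus-VKA percentages, rates and Kaplan-Meier curves to randomisation through day 180, the plan's last analysis time point before the switch. Day 90 would also avoid the crossover and needs no added follow-up, but it halves VKA time in the 15 controls from 7.4 to 3.7 patient-years.
2. Report data after day 180 separately, as an extension without a VKA control, with former controls shown apart from patients originally assigned to apixaban.
3. In Protocol 3.2, state that every randomised patient is observed for all outcomes and vital status to day 180, whether or not a major hemocompatibility event has occurred, and is analysed in the randomised arm. This concerns observation only and has no bearing on treatment after an event.
4. Reconcile Protocol 3.2, where continuing is offered as a choice, with Protocol 3.3.1 and the SAP, where the whole control arm is switched.

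The cost is wording in Protocol 2.2 and 3.2 and the SAP, plus event, rehospitalisation and outcome entries to day 180 on the existing data sheet for patients with an early event. If 10% to 20% have one (assumed), that is about 5 to 9 of 45. The downside is that extension data no longer feed the comparison with VKA.
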